### 10.1 Adverse Events

Specific adverse events of interest include symptomatic hypotension documented in the EHR. Hospitalizations related to heart failure will be captured during the study end using the ADHFD. If patients were removed from the dashboard at 6 months, a chart review will be performed to abstract missing data.

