### **5.4 Study Assessments**

Data for analysis will be pragmatically ascertained through the variables available in the ADHFD. The ADHFD data will be exported at baseline. To evaluate study outcomes, the ADHFD will be exported again to a secure Excel file 6-months after the last participant receives the intervention. The ADHFD data includes age, race, hospitalization risk scores, number of VA hospitalizations in the past 12 months, vital signs (weight, blood pressure, pulse), laboratory values (potassium, creatinine, BNP, eGFR), active GDMT prescriptions, and upcoming appointments. Sem-structured survey data will be captured by clinicians for only intervention patients. No interim analyses are planned. Longer term secondary evaluations will be evaluated at 1 and 2 year.

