### **7.3 Covariates and Subgroups**

Covariates of interest include age. We will evaluate age dichotomized based on the median of the trial participants and continuously in regression models. Race is categorized as White, Black, Hispanic, Asian, American Indian or Alaska Native. Heart rate will be used to dichotomize patients  $\leq 70$  and systolic blood pressure  $\leq 120$  mmHg. Renal function will be dichotomized for subgroups of patients with  $eGFR \geq 60$  ml/min/1.73 m^2.

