## 8.4 Demographic and Baseline Variables

Variables obtained from the ADHFD are available in **Table 2**.

Table 2: Baseline Variables from the Academic Detailing Heart Failure Dashboard	
Name	Legal name
Last 4 Social Security	-
Age	years
Race	White, Black, Hispanic, Asian, American Indian or Alaska Native
Weight	lbs
Primary Care Clinician	Assigned
3M Hospitalization Risk	Percent
3M Hospitalization Rank	Percentile
Heart Failure Hospitalizations	Last 12 months for any VA hospitalization.
Last Heart Failure Discharge	Date
Current Inpatient Status	Yes/No
Recent ED Visit	Last 14 days
Most Recent Left Ventricular Ejection Fraction (LVEF)	Last 3 years based on natural language processing variable construction
Last LVEF Documented Date	Date
Blood Pressure	Most recent recorded in the last year
Blood Pressure Date	Date
Pulse	Most recent recorded in the last year
Pulse Date	Date
Weight	Most recent in last 3 years
Weight Date	Date
Potassium	Most recent in last year
Potassium Date	Date
Magnesium	Most recent in last year
Magnesium Date	Date
Serum Creatinine	Most recent in last year
Serum Creatinine Date	Date
BNP	Most recent in last year
BNP Date	Date
NT-proBNP	Most recent in last year
NT-proBNP Date	Date
Digoxin	Most recent in the last year
Digoxin Date	Date
Estimated glomerular filtration (eGFR)	Race stratified estimates
eGFR Date	Date
ACE/ARB/ARNI	Medication name and dose *last fill must cover preceding 6 weeks **active, suspended, hold or provider hold orders ***Current non-VA medication
Beta-Blocker	"
Aldosterone Antagonist	"
SGLT2i	"
Allergies	To above medications only
Next Primary Care Appointment	Clinic name, date, and time
Next Cardiology Appointment	Clinic name, date, and time
Next Appointment	Next appointment for any clinic within 2 weeks.

Table 3: Expected Baseline Characteristics Presentation Template		
	Control	Intervention
Patient Characteristics		
Age	years	
Female	%	
Race	%	
White	%	
Black	%	
Asian	%	
AI/AN	%	
Mean BP	mmHg	
Systolic >120 mmHg	%	
Mean Pulse	rate	
Pulse >70	%	
Median Weight	lbs	
Mean eGFR		
Medications		
ACE/ARB/ARNI	%	
ARNI	%	
Beta-Blocker	%	
MRA	%	
SGTLT2i	%	
Diuretic	%	
Measurements		
Median Weight (IQR)	lbs	
Mean Pulse (SD)	Beats per minute	
Mean BP (SD)	SBP/DBP mmHg	
Mean Potassium (SD)	mmol/L	

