### S3: Clinician Documentation Form

Documentation survey which will guide clinician's chart review and patient conversation. The form will be password-protected and utilize checkbox and short answers for clinician ease.

Clinic Date	Clinician	Start Time	Homeless	Active Substance Use	Female	Last EF	Last cards appt	Last PCP appt
1/1/21	[name]	13:55	x	x	x	35-40%	1/1/21	1/1/21

Phone Call Time	NYHA Class	No Response
9 minutes	III	x

Reasons for no GDMT titration				
Prior intolerance	Prior adverse event	Patient declined	Patient concerned of side effects	Other
x	x	x	x	Cost

Actions Performed						
Number of Rx adjusted	Med adjustment	Labs ordered	Imaging / diagnostic tests	RTC	Patient Letter	Consults
3	Amlodipine stopped	x	x	x	x	x

Feedback	End Time	Comments
9	1415	Straight to voicemail

Clinician Documentation form definitions	
Clinic date	Date today, (mm/dd/yy)
Clinician	Name of clinician (Last, First)
Start Time	Military time at onset of pre-chart
Homeless	Is the veteran currently experiencing homelessness?
Active substance use	Is the veteran actively using substances?
Female	Sex as categorized in EHR
Last EF	Most recent left ventricular ejection fraction on transthoracic echocardiogram, %
Last cards appt	Date of last cardiology clinic visit, (mm/dd/yy)
Last PCP appt	Date of last PCP visit, (mm/dd/yy)
Phone Call Time	Duration of successful phone or video visit
NYHA Class	Based on patient's symptoms and chart review, (1-3)
No response	Indication if no response after 2 attempts
Patient requests later appointment	Indication if patient is interested in further discussion, but busy at this time. Check and order RTC cardiology
Reasons for no GDMT	
Prior intolerance	History of symptomatic bradycardia or hypotension on GDMT
Prior adverse event	History of hospitalization or angioedema related to GDMT titration. History of yeast infection while taking an SGLT2i inhibitor
Patient declined	Patient declined additional or higher doses of medications in the past
Patient concerned of side effects	Patient is concerned of side effects of GDMT
Other	Other reasons cited by patients or on chart review in the comments
Actions Performed	
# medication adjustments	Number of medications adjusted after this visit
Medication adjustment detail	Description of medication adjustment
Labs ordered	If laboratory tests ordered as part of today's plan
Imaging / diagnostic tests ordered	If imaging or diagnostic tests ordered as part of today's plan

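### Bradycardia is not a listed safety event, and the final-export pulse and blood pressure values have no planned safety comparison between arms

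*SAP*

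**What the plan says.** **Safety list.** SAP 10 has three items: acute kidney injury after a titration, reported by intervention clinicians for their own group; hospitalization for an adverse medication event related to the intervention; and the mortality difference. SAP 10.1 adds "Specific adverse events of interest include symptomatic hypotension documented in the EHR" and heart failure hospitalizations. Protocol 5 and 6 repeat this text. The SAP contents page lists a section 10.3 on other safety measures, but the body stops at 10.1.

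**Treatment and recognised intolerances.** Step 1 of the S1 guidance is to start or raise an ACE inhibitor or ARB, a beta-blocker, or both. Form S3 defines prior intolerance as "History of symptomatic bradycardia or hypotension on GDMT".

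**Data.** SAP 5.4 includes blood pressure and pulse among the dashboard variables. It exports the dashboard at baseline, and then "the ADHFD will be exported again to a secure Excel file 6-months after the last participant receives the intervention". Only the survey data are limited to intervention patients. Table 2 (SAP 8.4) defines pulse and blood pressure as "Most recent recorded in the last year", each with a date field.

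**Planned use of those values.** They appear in the baseline template (Table 3) and as subgroup splits in SAP 7.3, where "Heart rate will be used to dichotomize patients" and systolic pressure is split in the same way.

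**The concern.** The trial asks whether outreach raises a prescribing score, and part of that score is beta-blocker dose. A reader of the result will want to know what came with the extra prescribing. The investigators' own form recognises two haemodynamic intolerances, bradycardia and hypotension, but the safety plan names only hypotension.

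Little of the existing safety list gives a fair comparison between arms. Kidney injury is reported in one arm only. Medication-event hospitalization must be attributed to the intervention, so it has no usual-care counterpart. Charted symptomatic hypotension depends on someone asking: the S2 interview asks intervention patients about lightheadedness and passing out, and nobody makes that call in usual care. Extra detection could therefore look like extra harm.

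Pulse and blood pressure are measurements that need no symptom report and no attribution by unblinded staff. They are due to be exported in any case, and the plan does not say what will be done with the final values.

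**Working it through.** **1. Where bradycardia could be reported under the plan as written**

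| Route | Covers bradycardia? | Usual-care comparison? |
|---|---|---|
| Acute kidney injury (SAP 10) | No | No, intervention group only |
| Medication-event hospitalization (SAP 10) | Possibly: the examples are not exhaustive but do not name it | No, must be related to the intervention |
| Mortality (SAP 10) | Only a fatal case, not identified by cause | Yes |
| Heart failure hospitalization (SAP 10.1) | No | Yes |
| Any-cause hospitalization (SAP 4.2.2) | Only if admitted, not identified by cause | Yes |
| Events of interest (SAP 10.1) | Not listed; the wording is open-ended | Not stated |
| Form S3 | As history, a reason not to titrate | No, intervention patients only |

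No route defines non-hospitalized bradycardia, gives its source or compares it by arm.

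**2. Timing of the exported reading.** All patients are randomized at one time (SAP 5.3). The 150 intervention patients are then seen in lists of 10 to 15, which takes at least 150/15 = 10 to 150/10 = 15 half-day clinics. The final export comes 6 months after the last of these, with a one-year look-back. If the clinics span less than 6 months, the look-back reaches to before randomization, so a date restriction is needed. Randomization is the natural cut because usual-care patients have no clinic date. The price is that some intervention readings will predate the patient's own clinic.

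**3. Precision of a by-arm comparison of means.** The documents give no figure on this point; the stated 83% power concerns the optimization score and does not enter here. All inputs below except the 150 per arm are assumptions:

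- SD: pulse 12–14 bpm, systolic pressure 16–20 mmHg
- correlation of final with baseline value: 0.5
- coverage: 60–100% of 150 per arm, so m = 90 to 150

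SE = SD × √(2/m) × √(1 − 0.5²). The 95% CI half-width is 1.96 × SE. The difference detectable with 80% power (two-sided 5%) is 2.80 × SE.

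| | SD | m | SE | Half-width | Detectable |
|---|---|---|---|---|---|
| Pulse (bpm) | 12 | 150 | 1.20 | 2.35 | 3.4 |
| Pulse (bpm) | 12 | 90 | 1.55 | 3.04 | 4.3 |
| Pulse (bpm) | 14 | 150 | 1.40 | 2.74 | 3.9 |
| Pulse (bpm) | 14 | 90 | 1.81 | 3.54 | 5.1 |
| Systolic (mmHg) | 16 | 150 | 1.60 | 3.14 | 4.5 |
| Systolic (mmHg) | 16 | 90 | 2.07 | 4.05 | 5.8 |
| Systolic (mmHg) | 20 | 150 | 2.00 | 3.92 | 5.6 |
| Systolic (mmHg) | 20 | 90 | 2.58 | 5.06 | 7.2 |

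**4. Precision of a comparison of proportions.** With 150 per arm and an assumed rate p in each arm, the half-width is 1.96 × √(2p(1 − p)/150). This gives 3.2 percentage points at p = 2%, 4.9 at 5% and 6.8 at 10%. Power (two-sided 5%) is 29% for 2% against 5%, 38% for 5% against 10%, and 83% for 5% against 15%. Counts of bradycardia or of low readings will therefore be mainly descriptive.

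**The case against.** Several points on the other side stand, and they limit the conclusion.

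- **A reader might infer that non-hospitalized bradycardia would yield no reported events at all.** The documents do not go that far. The wording of SAP 10.1 is open-ended, and SAP 8 promises summaries of all continuous variables by arm, which could cover final pulse and blood pressure. What remains is that bradycardia has no definition or source, and a summary of means would not count patients with low values.
- **A reader might infer that titration ignores pulse and pressure, since the listed eligibility criteria set no limit on either.** S1 does steer the choice of drug by heart rate and systolic pressure, and S2 asks about home readings and symptoms. The gap is in reporting, not in clinical attention.
- **A reader might take a lower mean pulse in the intervention arm as harm.** It may simply show beta-blocker uptake.
- **Exported vital signs are not free of detection differences.** A reading also requires contact, and contact can differ by arm. Showing the number measured discloses this but does not remove it. One late reading will also miss an episode already managed.
- **A reader might think the dashboard's Allergies field ("To above medications only") could supply counts of the other reactions on S3, such as "History of hospitalization or angioedema related to GDMT titration".** Table 2 gives that field no date, and SAP 5.4 does not name it among the exported data. S2 asks intervention patients about past drug problems, which could prompt late entry of old reactions in one arm. Timing them would need chart review, so that count is not proposed.

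It can also be said that the choice of listed events is for the investigators, in a study the plan calls low risk. That bears on severity. It does not explain why one of the two intolerances named together on S3 is listed and the other is not.

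**Conclusion.** The point holds as a minor one. The intervention starts or raises beta-blockers, the plan's own form recognises symptomatic bradycardia, and the safety sections neither list it nor plan a by-arm safety comparison of the final pulse and blood pressure. The gap is clearest for pulse, because low blood pressure is partly covered by charted symptomatic hypotension.

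The primary analysis is unaffected. The benefit is a fuller and more comparable account of harm, not a powered safety test. The half-widths of about 2.4–3.5 bpm and 3.1–5.1 mmHg rest wholly on assumed SDs, correlation and coverage, and they describe means. They say nothing about how often bradycardia would occur, and the documents give no rate for it.

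**What to change.** 1. In SAP 10.1 and Protocol 6, add symptomatic bradycardia documented in the health record beside symptomatic hypotension. State that both are counted in both arms, by assigned arm, from the same source and by the same method.
2. Add one intention-to-treat table to SAP 10, using final-export pulse and systolic pressure dated after randomization. Report by arm:
   - the number with a reading
   - the mean difference adjusted for the baseline value, with a 95% CI
   - the proportion below a low-pulse and a low-pressure reporting cut-off, both fixed by the investigators before the final export
3. Label the table descriptive, with four limits stated: a lower mean may reflect treatment uptake; a single late reading misses transient events; some readings predate the patient's own clinic; and availability of a reading may differ by arm.

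**Cost.** SAP and protocol wording and one table, mostly from fields already due for export. Patients who have left the dashboard already undergo chart review (SAP 7.1 and 8.1), and pulse, pressure and their dates would be added to that abstraction. The symptomatic bradycardia count can share the record search needed for hypotension. If that search was meant for the intervention arm only, extending it to usual care is the main extra work. No dose, eligibility rule or patient management changes.

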## 11 Reporting Conventions

P-values  $\geq 0.001$  will be reported to 3 decimal places; p-values less than 0.001 will be reported as " $<0.001$ ". The mean, standard deviation, and any other statistics other than quantiles, will be reported to one decimal place greater than the original data. Quantiles, such as median, or minimum and maximum will use the same number of decimal places as the original data. Estimated parameters, not on the same scale as raw observations (e.g. regression coefficients) will be reported to 3 significant figures.

## 12 Quality Assurance of Statistical Programming

Code files for cleaning and analysis will be saved and dated for Stata 17.0 or greater. Co-investigators will evaluate baseline and outcome tables for anomalies. All output will include data and time, name of the code file that produced the analysis, and the author. Statistical reviewer will review trial raw and cleaned data, as well as Stata code and output files for all primary and secondary analyses.

## 15 Supplemental Material

S1: GDMT Guidance Document for LVEF ≤35%

### I. Make a recommendation

Step 1: patient not at target ACE/ARB or beta-blocker

Initiate/titrate up ACE/ARB and/or beta blocker

- If signs of volume overload or HR<70 → ACE/ARB
- If signs of euvoemia, HR>70, atrial fibrillation history, ventricular ectopy → Beta-blocker
- Age < 75, systolic BP>120 mm Hg, HR >70, normal renal function → Start both

*Tailored based on patient's profile and history.*

Step 2a: Transition ACE/ARB to ARNI

- Initiate ARNI once patient is taking equivalent dosing to lisinopril 20 mg daily

Step 2b: Initiate and titrate up aldosterone antagonist

- If K < 5 (helpful for hypokalemia)
- Well tolerated in low BP patients
- Check labs 3-7 days within initiation. Repeat labs monthly for the first 3 months.

Step 2c:

Initiate SGLT2i – empagliflozin 10mg daily

- Initiate earlier if A1C ≥7% or GFR 25-60 mL/min/1.73m^2 refer nephrology for SGLT2i
- Otherwise, add to cornerstone beta-blocker and RAAS inhibitor, ideally when dosing is stable.

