Prior to each ADHFD telehealth clinic (half-day clinic lasting 4 to 4.5 hours), clinicians will be sent a secure email that will include a password-protected Excel document of 15 patients with exported clinical summary data from the ADHFD. Clinicians will be instructed to chart-review patients and decide if an opportunity exists to further optimize the receipt of GDMT. Clinicians will also be given a document providing guidance on the sequence of GDMT optimization based on latest guidelines and VA policies (Supplement S1 GDMT Guidance Document). If a patient does not qualify for further optimization (i.e. chart documentation of prior intolerance, patient preference), a short note in the electronic health record (EHR) will document the chart review and inform the primary care clinician that based on chart review, no opportunity currently exists but they may consider further GDMT titration in the future. If a patient appears to have an opportunity for further titration, the clinician is encouraged to call the patient to see if they are available to discuss their HF care. If the patient agrees, a telehealth visit will take place over phone or switch to video. A formal telehealth cardiology visit will occur at the time of care. If the patient is interested but does not have time for a visit, a brief telephone note will be placed and a request for a future cardiology clinic visit will be requested. If a formal telehealth visit occurs, clinicians will be asked to inquire about key details around medication titration (**Supplement S2 Interview Guide**). The data from chart review and interviews will be documented on a password-protected Excel document (**Supplement S3 Clinician Documentation Form**). Any medication addition or titration will have indicated laboratory labs ordered per usual care. Lastly, clinicians will also be asked to administer a short survey with each participant based on a template at the end of the call proactive phone call (**Supplement S2 Interview guide**). Primary care and regular cardiology clinicians will be notified of any changes in medication management in the EHR. The study's lead (BZ, AV) will be available by phone to answer questions or problems that arise during the clinic. Supervision of patient encounters by clinical pharmacists, medical trainees, or advanced practice nurse practitioners and study protocols will be BZ as the licensed and boarded general cardiologist.

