## 10 Safety Analysis

Clinicians involved with the intervention will report acute kidney injury (AKI) defined as 25% decrease in GFR from baseline on follow-up labs (1-week for MRA and 1-2 weeks for ACE/ARB/ARNI) after a successful medication titration within the intervention group. Laboratory alerts will be followed by pilot study clinicians. Hospitalization related to adverse medication event (e.g. symptomatic hypotension, AKI, hyperkalemia) related to the intervention. Difference in mortality between intervention and usual care.

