### Next steps

- Order medications
- Follow-up appointment
- Required labs
- BMP in one week (MRA), 1-2 weeks (ACE/ARB/ARNI)

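### The guidance sheet asks for monthly MRA labs that the interview guide and the AKI rule do not name, so non-hospitalized AKI first seen on them may not be counted

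*SAP*

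**What the plan says.** Three places in the SAP give laboratory timing after an MRA is started or titrated. The Protocol repeats all three, in Section 5 and in its own supplements S1 and S2.

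- **S1 guidance document, Step 2b:** "Check labs 3-7 days within initiation. Repeat labs monthly for the first 3 months".
- **S2 interview guide, Next steps:** "BMP in one week (MRA), 1-2 weeks (ACE/ARB/ARNI". No repeat lab is listed.
- **SAP Section 10:** intervention clinicians report "acute kidney injury (AKI) defined as 25% decrease in GFR from baseline on follow-up labs (1-week for MRA and 1-2 weeks for ACE/ARB/ARNI", and the rule applies "after a successful medication titration within the intervention group".

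Three other statements bear on the point.

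- SAP Section 5.1 says "Any medication addition or titration will have indicated laboratory labs ordered per usual care", which sets no timetable.
- Section 10 says "Laboratory alerts will be followed by pilot study clinicians", with neither a time limit nor a counting rule.
- Section 10 lists as a separate safety item "Hospitalization related to adverse medication event (e.g. symptomatic hypotension, AKI, hyperkalemia) related to the intervention", with no lab window attached.

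**The concern.** Under SAP Section 5.1 the same clinicians receive S1 and use S2 when a telehealth visit takes place, and each intervention patient gets a single chart review. Labs are therefore largely set at that one contact. A clinician working from S2's closing list has no prompt to order the monthly labs. A clinician working from S1 may order labs that the AKI rule does not clearly count.

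What is at stake is the AKI count in the safety report. AKI is reported by the clinicians, in the intervention arm only. If the rule is applied as literally written, a low count could reflect a narrow window rather than renal safety, and ascertainment could differ between clinicians.

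**Working it through.** The plan gives no figure to reproduce here, so the check sets the schedules side by side. S1 counts from initiation and Section 10 from a successful titration. I take the start of the MRA as day 0 for both.

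| Source | First MRA lab | Repeat MRA labs | ACE/ARB/ARNI lab |
|---|---|---|---|
| S1, Step 2b | days 3 to 7 | monthly for 3 months | no timing given in S1 |
| S2, Next steps | one week | none listed | 1 to 2 weeks |
| Section 10, AKI rule | one week | none listed | 1 to 2 weeks |
| SAP 5.1 | per usual care | no timetable | per usual care |

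1. **S2 against Section 10.** The timings are identical for both drug groups. S1 is the only outlier.
2. **First check.** The S1 window of days 3 to 7 contains day 7, so one lab on day 7 satisfies all three texts. A lab on day 3, 4, 5 or 6 fits S1 but not a strict reading of one week.
3. **Monthly checks.** With a 30-day month (an assumption) they fall on days 1 × 30 = 30, 2 × 30 = 60 and 3 × 30 = 90. With months of 28 to 31 days they fall on days 28–31, 56–62 and 84–93. The widest window in the AKI rule, the one for ACE/ARB/ARNI, ends at 2 × 7 = 14 days. All three monthly labs lie beyond it on either assumption.
4. **Count.** S1 implies 1 early + 3 monthly = 4 MRA checks. Section 10 names one MRA time point, which leaves 4 − 1 = 3 of 4 outside it.
5. **Could another data source recover the event?**
   - AKI leading to an intervention-related hospitalization is a separate item without a lab window, so it is captured.
   - Following laboratory alerts is clinical follow-up. Nothing says that an alert becomes a counted AKI.
   - The dashboard is exported at baseline and 6 months after the last participant's intervention (SAP 5.4). Table 2 lists serum creatinine as the most recent value in the last year, so an export holds one value and not a series. If the MRA starts at the study contact, the last monthly lab precedes the final export by at least about 6 − 3 = 3 months. A fall that had recovered by a later test would not show.
   - Chart review is planned for data missing from the dashboard that the primary or secondary analyses need (SAP 7.4) and for patients who have left the dashboard (SAP 10.1). Neither is a search for interim GFR values.

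What remains uncovered is non-hospitalized AKI first seen on a monthly MRA lab.

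**The case against.** The strongest reply is that the texts are complementary. S1 guides the sequence of therapy, S2 is an end-of-call list that names the first lab, and naming a first lab does not cancel later ones. The parenthesis in the AKI rule can be read as the expected timing of labs rather than a cut-off, since it does not say that only those labs count. A short window also has a rationale, because it ties a GFR fall to the titration.

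Much of this stands, and it limits what can be claimed. Four stronger readings are tempting, and the documents do not support them.

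- A reader might infer that all three texts disagree. They do not: S2 and Section 10 match, and S1's first check overlaps both.
- A reader might infer that AKI on monthly labs is certain to go uncounted. The parenthesis is ambiguous, and hospitalized AKI has its own route, so the supportable wording is that it may not be counted.
- A reader might take three labs of four as the share of AKI events missed. It counts scheduled labs. The documents give no number of MRA starts and no AKI rate over time.
- A reader might conclude that AKI should be counted up to final evaluation. That exceeds S1's own three months. It also gives patients seen early a longer window than those seen late, and adds late GFR changes from other causes with no control-arm count to set against them.

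The reply does not remove the ambiguity. The SAP does not say whether the parenthesis is a cut-off, and no other route clearly counts the event.

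**Conclusion.** The point holds as a mismatch between S1 on one side and S2 with Section 10 on the other, confined to the monthly MRA labs and, less importantly, to first labs taken on days 3 to 6. Non-hospitalized AKI first seen on a monthly lab that the plan itself requests falls outside the AKI definition as literally written and may not be counted.

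In size, three of four scheduled MRA checks are affected, in intervention patients who start an MRA. With 300 patients allocated 1:1, that is at most 300 / 2 = 150 patients. The number of events cannot be estimated from the documents. The conclusion rests on taking MRA initiation as day 0 and a month as 28 to 31 days. It concerns a descriptive safety measure reported in the intervention arm only. The primary analysis, the sample size and the between-arm comparisons are unaffected.

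**What to change.** 1. The clinical investigators should reconcile S1 Step 2b, the S2 Next steps list and SAP Section 10 to a single MRA lab schedule, and carry the result into Protocol Section 5 and the Protocol's supplements. Which schedule is right is a clinical decision and is left to them.
2. Section 10 should then define AKI as a 25% GFR decrease on any follow-up lab within that reconciled schedule, including early labs and any monthly labs that are retained.
3. Each AKI event should be reported with its date and its time from titration, so that early and later events can be separated.

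The cost is a few sentences in the two supplements and the safety section, repeated in the Protocol, plus a place to record the event date. The S3 form notes that labs were ordered but has no field for a result. The AKI count may rise, and later events are harder to attribute to the titration because the control arm has no AKI count. Reporting time from titration lets readers see this, although it does not supply a comparator.
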